1.3.3.1.1 Safety Data from Ongoing MM-398-07-02-03 Study

A Randomized, Open-label Phase 2 Study of Nanoliposomal Irinotecan (nal-IRI)-containing Regimens versus nab-paclitaxel plus Gemcitabine in Patients with Previously Untreated, Metastatic Pancreatic Adenocarcinoma (NCT02551991)

This study is an open-label, phase II study to assess the safety, dose-limiting toxicities (Part 1A only), tolerability, and preliminary efficacy of irinotecan liposome injection in combination with oxaliplatin+5-FU/LV in subjects with metastatic pancreatic adenocarcinoma who have not received prior systemic anti-tumor therapy. The study comprises an initial dose exploration (Part 1A) followed by dose expansion (Part 1B ongoing in the extension phase) of the irinotecan liposome injection+ oxaliplatin+5-FU/LV regimen.

For the 56 subjects treated, all (100.0%) had treatment-emergent adverse events (TEAEs). There were nine TEAEs that were defined as Dose Limiting Toxicities (DLTs) that were reported by five subjects across the four dose exploration cohorts (diarrhea, n=2; vomiting, anal fissure, anal inflammation, proctalgia, neutropenic infection, neutropenic sepsis, and febrile neutropenia, all n=1), including one subject treated in Part 1A- Cohort B who was included in the pooled analysis (febrile neutropenia)

Treatment-related TEAEs Grade 3 or higher were reported by 41 of 56 subjects, including 22 subjects from the pooled analysis of 32 subjects treated with irinotecan liposome injection 50 mg/m2+LV 400 mg/m2+5-FU 2400 mg/m2 and oxaliplatin 60 mg/m2. The TEAEs included: neutropenia, n=10; febrile neutropenia, hypokalemia, both n=4; diarrhea, nausea, both n=3; anemia, vomiting, both n=2, with no reported Grade 3 or higher fatigue or peripheral neuropathy.

SAEs were reported by 34 of the 56 treated subjects, including 17 of the 32 subjects in the pooled analysis, with 23 subjects reporting treatment-related SAEs. In the pooled analysis, 10 of the 32 subjects had treatment-related SAEs: nausea, febrile neutropenia, both n=3; diarrhea, vomiting, both n=2; colitis, enterocolitis, stomatitis, anemia, pneumonia, and pyrexia, all n=1. At the data cut-off there were no treatment-related TEAEs leading to death.

There were 19 subjects who reported TEAEs leading to discontinuation (including eight subjects in the pooled analysis), with 39 subjects requiring dose adjustment due to AEs (including 26 subjects in the pooled analysis).

Please refer to the current version of the Investigator's Brochure (IB) for complete safety information regarding this drug.

1.3.3.2 Efficacy

The efficacy data for irinotecan liposome injection are described in detail in the investigator brochure. The efficacy profile of treatment with irinotecan liposome injection, in combination with 5- fluorouracil and leucovorin, in patients with metastatic pancreatic cancer previously treated with gemcitabine is derived primarily from the single phase 3 study (Study Number MM 398- 07-03-01, NAPOLI-1), which was initiated following the promising results of a single-arm, phase 2 study of irinotecan liposome injection as a single-agent in the same patient population (Study PEP0208).

Overall in Study PEP0208, 30/40 (75.0%) patients in the Per Protocol population achieved the 3month survival primary efficacy endpoint (95% CI: 58.8-87.5%) while being treated with irinotecan liposome injection. In addition, 6-month survival was achieved by 17/40 (42.5%) patients and 12-month survival by 10/40 (25.0%) patients.

The basis for the US marketing authorization application of irinotecan liposome injection, in combination with 5-fluorouracil and leucovorin in patients with metastatic pancreatic cancer previously treated with gemcitabine, was the NAPOLI-1 study. The NAPOLI-1 study tested the clinical efficacy and safety of two potentially new treatment options, irinotecan liposome injection monotherapy and irinotecan liposome injection+5FU/LV combination therapy, in pairwise comparison to an active control arm, consisting of 5-FU and leucovorin.

The baseline characteristics of the patient population in the study were considered representative of a pretreated, metastatic pancreatic cancer population, similar to that found in clinical practice, and were balanced across treatment groups. Of 577 screened, 417 patients were randomized and included in the ITT population.

The combination of irinotecan liposome injection+5-FU/LV achieved a median overall survival (OS) of 6.1 months compared to 4.2 months for the control arm of 5-FU/LV alone. The NAPOLI-1 study demonstrated a clinically relevant and statistically significant (p=0.012) superiority of OS in patients receiving the irinotecan liposome injection+5-FU/LV combination over the 5-FU/LV control arm. Additionally, sensitivity analyses supported this primary OS analysis of the irinotecan liposome injection+5-FU/LV combination. The OS benefit was present (or could not be ruled out) in all pre-specified subgroups.

Among the secondary endpoints, PFS, ORR, TTF and CA 19-9 response rate demonstrated statistically significant superiority for the irinotecan liposome injection+5-FU/LV combination over the 5-FU/LV control arm.

1.4 Rationale

Clinical studies have documented the therapeutic benefits of encapsulated liposome anti-cancer drugs such as doxorubicin and vincristine [Duggan et al, 2011; Pathak et al, 2014]. Irinotecan is a member of the camptothecin class of topoisomerase I (TOPO1) inhibitors, whose principal mechanism of action leading to cell death is through DNA damage after replication-fork collisions with transiently trapped drug-TOPO1-DNA cleavage complexes, thus emphasizing the length of drug exposure as an important driver for cytotoxicity of camptothecins [Pommier, 2006; Pommier, 2009]. It has shown significant activity in a variety of tumor types. Promising response rates have been observed in many malignancies such as colorectal, non-small cell lung, and small cell lung cancers. However, at higher dosage, irinotecan causes severe diarrhea and myelosuppression, which are recognized as the dose-limiting toxicities and limit the use of more aggressive irinotecan therapy.

Irinotecan liposome injection is a novel liposomal formulation of irinotecan, designed to maintain or increase its anti-tumor efficacy. Irinotecan liposome injection has also been known as PEP02, MM-398, and nal-IRI. Irinotecan liposome injection has been studied in patients with solid tumors, including cervical cancer, gastric cancer, pancreatic cancer and colorectal cancer. Disease areas currently being studied by Ipsen Biopharmaceuticals include metastatic pancreatic cancer, breast cancer, colorectal cancer and pediatric solid tumors, including Ewing's sarcoma, rhabdomyosarcoma, neuroblastoma and osteosarcoma. Disease areas currently being studied in investigator-sponsored clinical studies include pancreatic cancer, glioma (intravenous and convection-enhanced local delivery) and breast cancer.

The Food and Drug Administration (FDA)-approved liposomal irinotecan (nal-IRI) has been shown to increase and prolong intratumoral levels of both irinotecan and its active metabolite SN-38 (Wang-Gillam et al. Lancet 2016; 387: 545-557). These data suggest a therapeutic advantage of nal-IRI over the conventionally used irinotecan. Currently, the combination of nal-IRI with 5-fluorouracil and leucovorin is a second line treatment approved by the FDA for metastatic pancreatic adenocarcinoma that has progressed following treatment using nabpaclitaxel and gemcitabine. Whether nal-IRI in combination with oxaliplatin, 5-fluorouracil, and leucovorin improves tumor response and resection rate for patients with LAPC has not been investigated. This proposed study is aimed to test the hypothesis that combination of nal-IRI with oxaliplatin, leucovorin, and 5-fluorouracil (FOLFOX-nal-IRI) is a tolerable systemic therapy that improves tumor response, resection rate, and quality of life for patients with LAPC.

2. STUDY OBJECTIVES AND ENDPOINTS

2.1 **Objectives**

2.1.1 Primary Objective

Estimate the disease control rate (DCR) at 24 weeks for nal-IRI in combination with oxaliplatin, leucovorin, and 5-fluorouracil (FOLFOX-nal-IRI), in subjects with locally advanced pancreatic carcinoma (for the subjects whose tumors remain unresectable following 12 cycles of FOLFOX-nal-IRI).

2.1.2 Secondary Objectives

- Describe the objective response rate (ORR) at 8 weeks, 16 weeks, and 24 weeks following starting FOLFOX-nal-IRI.
- Describe the stable disease rate (SDR) at 8 weeks, 16 weeks, and 24 weeks following starting FOLFOX-nal-IRI.
- Describe the proportion of subjects able to undergo surgical resection of tumor.
- Describe the response of serum CA 19-9 after every 2 cycles (every 4 weeks) following starting FOLFOX-nal-IRI.
- Determine progression-free survival (PFS).
- Determine overall survival (OS).
- Describe safety and tolerability of (FOLFOX-nal-IRI).
- Describe quality of life after every 4 cycles (every 8 weeks) following starting FOLFOXnal-IRI.

2.1.3 Exploratory Objectives

- Determine FOLFOX-nal-IRI induced DNA damage/repair and apoptosis in biopsied and surgically resected tumor tissues.
- Determine DNA damage in blood-based biopsies prior to treatment and following every 4 cycles (8 weeks) of treatment.
- Determine the tumor molecular profile prior to initiation of chemotherapy and correlate with treatment responses.
- Determine the metabolic profiles of plasma prior to treatment and following every 4 cycles (8 weeks) of treatment.
- Examine the inter-institutional variability of the overall resectability rate.

2.2 Endpoints

2.2.1 Primary Endpoint

Disease control rate (DCR) as determined by the proportion of subjects with complete response, partial response, or stable disease, as defined by RECIST 1.1, at 24 weeks following initiation of FOLFOX-nal-IRI (for the subjects whose tumors remain unresectable following 12 cycles of FOLFOX-nal-IRI).

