5. TREATMENT PLAN

This is a phase II, single-arm, open-label, clinical study to investigate the efficacy and tolerability of a combination of liposomal irinotecan (nal-IRI) with oxaliplatin, leucovorin, and 5-fluorouracil (FOLFOX-nal-IRI) for treatment of patients with locally advanced pancreatic carcinoma (LAPC). Each subject will be screened for eligibility and if eligible will be registered to the study. Within 28 days of screening, the consented subjects will have a central venous access device placed and then start treatment.

Subjects will receive FOLFOX-nal-IRI every 2 weeks as described below. Tumor response/surgical assessment will be evaluated after every 4 cycles of treatment with contrastenhanced CT scans using RECIST 1.1 criteria. If the tumor becomes surgically resectable and the subject is a surgical candidate as determined by a multidisciplinary team at any point, the subject should be removed from study treatment and undergo surgery (at which point he/she would enter survival follow-up). If the tumor remains unresectable and there is no tumor progression, each subject will be treated up to a total of 12 cycles of FOLFOX-nal-IRI. Oxaliplatin could be discontinued for Grade 3 or 4 neuropathy, and the subject would still be considered on study.

Following treatment with 12 cycles of FOLFOX-nal-IRI (for those patients not offered radiotherapy), if the tumor remains unresectable, the subjects may receive further treatment (chemotherapy using the same regimen or of the treating physician's choice, or chemoradiation therapy) or observation as determined by the treating physician. Regardless of choice at this point, patients should be followed for survival.

5.1 **Pre-medication and Hydration**

Premedication and hydration will be provided as per institutional standards. It should be noted that the regimen is considered moderately emetogenic. A corticosteroid and anti-emetic will be administered at least 30 minutes prior to infusion of nal-IRI and oxaliplatin or as per institutional standards.

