6.2.3 Dose Reduction of 5-Fluorouracil

- a. 5-fluorouracil will be held for any of the following:
 - Grade 3 or 4 diarrhea
 - Grade 2 or 3 palmar-plantar erythrodysesthesia (hand-foot syndrome)
 - Grade 3 or 4 mucositis
 - Grade 4 myelosuppression
- b. Upon resolution or improvement to Grade 1 diarrhea, mucositis, myelosuppression, or palmar-plantar erythrodysesthesia, resume administration of 5-fluorouracil at 1,920 mg/m² for first occurrence, or 1,440 mg/m² for second occurrence.
- c. 5-fluorouracil will be discontinued following development of any of the following adverse reactions:
 - Angina, myocardial infarction/ischemia, arrhythmia, or heart failure in patients with no history of coronary artery disease or myocardial dysfunction
 - Hyperammonemic encephalopathy
 - Acute cerebellar syndrome, confusion, disorientation, ataxia, or visual disturbance

6.3 **Protocol Therapy Discontinuation**

In addition to discontinuation from therapy related to toxicities as outlined above, a subject will also be discontinued from protocol therapy and followed up per protocol under the circumstances outlined below. The reason for discontinuation of protocol therapy will be documented on the electronic case report form (eCRF).

• Documented disease progression

- The treating physician thinks a change of therapy would be in the best interest of the subject
- The subject requests to discontinue protocol therapy, whether due to unacceptable toxicity or for other reasons
 - If a subject decides to prematurely discontinue protocol therapy ("refuses treatment"), the subject should be asked if he or she may still be contacted for further scheduled study assessments. The outcome of that discussion should be documented in both the medical records and in the eCRF.
- A female subject becomes pregnant
- If protocol therapy is interrupted for ≥ 28 days.

6.4 **Protocol Discontinuation**

If a subject decides to withdraw from the study (and not just from protocol therapy) all efforts should be made to complete the final study assessments. The site study team should contact the subject (ex. telephone, telehealth, clinic visit, etc.) to determine the reason for the study withdrawal. If the reason for withdrawal is an adverse event, it will be recorded on the eCRF.

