9.8.4 Disease Control Rate

The disease control rate is the proportion of all subjects with stable disease (SD) for 8 weeks, or partial response (PR), or complete response (CR) according to RECIST 1.1, from the start of treatment until disease progression/recurrence (taking as reference for progressive disease the smallest measurements recorded since the start of treatment).

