12.2 Endpoints

12.2.1 Definition of Primary Endpoint

Disease control rate (DCR) as determined by the proportion of subjects with complete response, partial response, or stable disease, at 24 weeks following initiation of FOLFOX-nal-IRI.

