12.3 Sample Size and Accrual

It is assumed that LAPC patients have a DCR of 45% with standard of care, whereas LAPC patients will have DCR rate of 75% under the protocol in this study. A minimax Simon's two-stage design will be implemented with 12 patients evaluated in the first stage. If 5 or fewer responses are observed from these 12 patients, then the study will be stopped for futility. Otherwise, an additional 13 patients will be added yielding a total sample size of 25 patients. The study will be considered successful if 16 or more responses are observed in the 25 patients. This design comprises a type 1 error rate of 5% and a power of 80% when the true DCR is 75%.

Therefore, this study seeks to recruit 12 to 25 patients depending on results of the first stage evaluation. Assuming approximately 10% of the patients would not be evaluable, the target sample size is 28 patients.

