12.5 Assessment of Efficacy

This will comprise all subjects who receive at least one dose of trial drug and either undergo at least one post-baseline assessment or die before any evaluation.

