12.7 Interim Analysis/Criteria for Stopping Study

A single interim analysis for futility will take place when the 12th subject has completed 6 months of follow-up. The proportion of subjects that is tumor progression-free at 6 months will be assessed along with other efficacy and safety data in making the determination if the study should continue. If 5 or fewer responses are observed from these 12 patients, then the study will be stopped for futility. Otherwise, an additional 13 patients will be added yielding a total sample size of 25 patients. Accrual will continue during the interim analysis. Recruitment will be halted if futility is determined.

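### Sections 2.1.1 and 2.2.1 confine the primary 24-week DCR to a subset selected largely by outcome; 12.2.1, 9.8.4 and 12.7 differ, and resected subjects have no single consistent score

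*Combined protocol and SAP*

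**What the plan says.** The primary endpoint is described in several places that do not agree.

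- **Sections 2.1.1 and 2.2.1:** DCR at 24 weeks, "for the subjects whose tumors remain unresectable following 12 cycles of FOLFOX-nal-IRI".
- **Section 12.2.1:** the proportion with complete response, "partial response, or stable disease, at 24 weeks following initiation of FOLFOX-nal-IRI", with no limit on which subjects count.
- **Section 9.8.4:** "The disease control rate is the proportion of all subjects with stable disease (SD) for 8 weeks", or PR or CR, with no 24-week landmark.
- **Section 12.7:** at the interim, "The proportion of subjects that is tumor progression-free at 6 months will be assessed"; the same paragraph then counts responses among 12 patients.
- **Section 12.5:** the efficacy set is "all subjects who receive at least one dose of trial drug and either undergo at least one post-baseline assessment or die before any evaluation".

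The synopsis and section 12.6.1 name DCR as the primary endpoint without a time point.

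Two other sections decide who reaches 12 cycles. Section 6.3 lists "Documented disease progression" among the reasons for ending protocol therapy. Section 5 says that once the tumor is resectable and the patient is a surgical candidate, "the subject should be removed from study treatment and undergo surgery", followed by survival follow-up. On numbers, section 12.3 says: "Assuming approximately 10% of the patients would not be evaluable, the target sample size is 28 patients".

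**The concern.** A two-stage rule on 12 and then 25 subjects needs one countable set and one definition of success. Twelve 14-day cycles last 24 weeks, so a subject who has completed them has largely shown the disease control that the endpoint is meant to measure. Removing subjects who progressed earlier raises the reported DCR. Removing controlled subjects who went to surgery lowers it. The net bias is unknown.

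Resected subjects get a different answer in each section. Under 2.2.1 they are excluded. Under 12.2.1 with 12.5 they are in the set, but nothing says what their 24-week status is. Under 9.8.4 they could count as controlled on the strength of scans before surgery. In an open-label single-arm trial, leaving this open means the reading could be chosen once the data are known.

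**Working it through.** **1. The plan's own rule.** Inputs from 12.3: null 45%, target 75%; stop at 5 or fewer of 12; succeed at 16 or more of 25.

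P(success) = sum over x = 6 to 12 of Bin(x; 12, p) × P(Bin(13, p) ≥ 16 − x).

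- p = 0.45: 0.043. This respects the stated 5%.
- p = 0.75: 0.925. The stated 80% does not reproduce at 75%; the rule gives 0.804 at p = 0.70. This is a separate matter and is conservative.

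**2. Literal restriction, resections ignored.** The documents give no progression curve, so one is assumed: Weibull with shape k from 1 to 2. A subject is taken as countable if progression-free at the week-16 scan. Then S16 = S24^((16/24)^k), and the DCR shown in the subset is S24/S16.

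| True 24-week DCR | k | S16 | DCR shown | Expected countable of 28 | P(25 or more countable) |
|---|---|---|---|---|---|
| 45% | 1 | 0.587 | 77% | 16.4 | 0.0005 |
| 45% | 1.5 | 0.647 | 69% | 18.1 | 0.003 |
| 45% | 2 | 0.701 | 64% | 19.6 | 0.016 |
| 75% | 1 | 0.825 | 91% | 23.1 | 0.25 |
| 75% | 1.5 | 0.855 | 88% | 23.9 | 0.41 |
| 75% | 2 | 0.880 | 85% | 24.6 | 0.56 |

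**3. Effect on alpha.** Let K be Bin(N treated, S16), count up to 25 of them, and require 6 or more of the first 12 counted and 16 or more in all.

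- N = 25 treated, restriction applied: 4.4% at all three shapes, against 4.3% without it.
- N = 28 treated, restriction applied: 13.5%.
- N = 28 treated, no restriction, cut-off 16: 12.2%.

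A success must still be a controlled subject, so removing progressors cannot create one. It only makes the interim look easier to pass. Nearly all of the rise comes from applying a cut-off of 16 to 28 treated subjects.

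**4. Resected subjects.** Assume a share f of all subjects is resected before week 24, all of them otherwise controlled, with true control of 75% including them. Scored as failures, p = 0.75 − f. Excluded and replaced, p = (0.75 − f)/(1 − f).

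| f | p as failures | Power | p excluded and replaced | Power |
|---|---|---|---|---|
| 5% | 0.70 | 80% | 0.737 | 90% |
| 10% | 0.65 | 62% | 0.722 | 87% |
| 20% | 0.55 | 24% | 0.688 | 76% |

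Counted as controlled, power stays at 92.5% for any f.

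**5. The 8-week definition.** If 45% is a 24-week rate and the hazard is constant, the 8-week rate is 0.45^(8/24) = 0.766, and the rule passes with probability 0.949.

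**The case against.** The parenthetical may have been meant only as a timing note, and section 12 may be intended to govern. Nothing in the documents says either. Even if both were granted, the 8-week definition in 9.8.4 and the missing status rule for resected subjects would remain.

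Several stronger readings are tempting and are not supported:

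- **That the restriction itself raises the false-positive rate to 13.5%.** Step 3 shows it does not; with 25 treated, alpha is about 4.4%.
- **That alpha reaches 59-95%.** Those are the values if enrolment ran on until 25 subjects were countable, which would take about 36-43 treated (25/S16). The plan sets 28, and no section allows enrolment to continue past that.
- **That 25 countable subjects could not be reached.** That is nearly so at a true 45%, but at the planning value of 75% they would be reached 25-56% of the time.
- **That resected subjects are never scored.** Section 2.2.1 read literally excludes them, 9.8.4 could count them, and the secondary resectability rate includes them. What is missing is one consistent rule.
- **That 9.8.4 would pass an ineffective regimen 95% of the time.** This holds only if the 45% benchmark is a 24-week rate. Section 12.6.1 takes its reference figures from published response and stable-disease rates and gives no time point. Section 9.8.4 is also a general definition, while 2.1.1, 2.2.1 and 12.2.1 all name 24 weeks.

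It is also fair that section 1.1 calls resection rare. At 10% resected, excluding and replacing those subjects leaves power at 87%, above the stated 80%. Scoring them as failures does not: power is 62%. Improving the resection rate is part of the hypothesis in section 1.4.

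**Conclusion.** The concern holds as a conflict in the definition of the primary endpoint, and it should be resolved before the interim. The conflict is in the text and rests on no assumption: sections 2.1.1 and 2.2.1, 12.2.1, 9.8.4 and 12.7 do not give one population, one time point and one treatment of resected subjects.

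Its size does rest on assumptions. Under Weibull shapes 1 to 2 with resections ignored, the literal subset overstates a true 45% as about 64-77%, and 25 countable subjects would be reached within 28 treated at most 2% of the time. With all 25 kept, the scoring of resected subjects alone moves power from 92.5% to 62% at an assumed 10% resected. A reader might infer that the restriction breaks type 1 error control. Within 25 treated it does not; a rise to 12-14% would come from applying the cut-off of 16 to 28 treated.

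**What to change.** - Delete the parenthetical in 2.1.1 and 2.2.1.
- State in 9.8.4 and 12.7 that the primary DCR is CR, PR or SD at the 24-week assessment, as in 12.2.1.
- Use one denominator that the outcome does not define: treated subjects. Apply the bounds to the first 12 and first 25 of them, and say what the 10% allowance then covers.
- Do not apply the cut-off of 16 to 28 treated (alpha 12.2%). If all 28 are analysed, a cut-off of 18 gives alpha 3.1% and power 92.7%.
- Before the interim, fix one scoring rule for subjects resected without prior progression. It should need documented status at week 24 and treat missing status as for every other subject. Report the opposite scoring as a sensitivity analysis.
- State the time point of the 45% benchmark and whether it counts resections. Restate alpha and power.

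**Cost.** The reported DCR will be lower than under the literal restriction. If a missing 24-week assessment counts as not controlled, with missingness unrelated to outcome, p = 0.75 × (1 − m): power is 84% at 5% missing and 72% at 10%, and it falls below 80% at about 7%. That matters because 12.3 itself allows for about 10% not evaluable. Holding 80% at 10% missing would take about 31 treated with 19 or more controlled (alpha 4.8%). Compared with 12.5, subjects who leave alive with no post-baseline assessment become failures. Some subjects off treatment would need a week-24 assessment that calendar footnote 7 and section 7.2 do not now require.
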